**6.3        Subject Withdrawal**

Subjects are free to discontinue the study at any time, for any reason, and without prejudice to further treatment. The investigator may remove a subject if, in the investigator's judgment, continued participation would pose unacceptable risk to the subject or to the integrity of the study data. All procedures for early termination must be completed. Reasons for removal or withdrawal may include:

- Withdrawal of consent
- Administrative decision by the investigator or sponsor
- Ineligibility
- Significant protocol deviation
- Subject noncompliance
- Safety concern by the investigator or sponsor
- Lost to follow-up

Subjects who are withdrawn for reasons other than safety issues may be replaced at the discretion of the sponsor and investigator.

In the event of a subject's withdrawal, the investigator will promptly notify the medical monitor and will make every effort to complete the EOS assessments. All withdrawn subjects with ongoing clinically significant clinical or laboratory findings will be followed until the finding is resolved or medically stable; reasonable attempts will be made to follow-up with subjects.

CONFIDENTIAL

Subjects will be withdrawn from the study if they meet specific stopping criteria for the study (see [Section 6.4](#)).

#### **6.4 Early Termination of Study**

##### **6.4.1 Cohort Stopping Criteria**

Dosing in a cohort will be suspended if any of the following occur:

- 2 or more subjects in the dose cohort meet individual stopping criteria ([Table 6.1](#))
- 2 or more subjects in the dose cohort experience treatment-related clinically relevant (ie, moderate and/or severe) AEs
- 1 or more subjects in the dose cohort experience a treatment-related SAE

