#### **3.6.2 Rationale for Study Design**

This is a Phase 2b prospective, open-label study designed to evaluate the safety, tolerability, PK, and pharmacodynamics (PD) of the FAST PV and mGFR Technology in healthy adult subjects and patients with renal impairment.

CONFIDENTIAL

Male and female subjects will be enrolled in the study. As no sufficient data are available on a potential influence of the investigational medicinal products on embryo-fetal development, female subjects must be of non-childbearing potential or must provide confirmation of a known and medically acceptable contraception method. Reproductively active men must agree to either practice abstinence or utilize adequate contraception.

Subject safety will determine the progression or discontinuation of the study. In rare cases, dextran products have been documented to produce anaphylactic reactions in humans, and the onset of symptoms is documented to be acute. Though the FAST VFI is a substituted dextran product, and has shown little evidence of antigenicity in nonclinical studies, a cautious approach to dosing sequence is proposed.

The duration of confinement and medical surveillance are considered adequate to ensure safety of the subjects.

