
#### 5.1.1 Interim Safety Data Review

A safety review committee (SRC) will be convened at predetermined interval(s) to review safety data from this study. The SRC will consist of, at minimum, the investigator, medical monitor, and sponsor medical representative. If warranted, the committee may expand to include PK, PD, and other relevant subject matter experts. The SRC may request additional data including relevant PK and PD data, if necessary, and may recommend adequate safety measures including early termination of the study based on the discretion of the investigator or the criteria set forth in **Section 6.4**. However, should there be no AEs of clinical significance and no evidence of signals upon review of the safety data, subsequent dosing of subjects and patients will be permitted.

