## 9.4 Reporting Serious Adverse Events

In the event of any SAE reported or observed during the study, whether or not attributable to the study drug, site personnel will report it immediately by telephone to the medical monitor AND to the SAE hotline at ICON in accordance with procedures described in the study reference manual and/or SAE study-specific procedure. Site personnel will follow up with a faxed written report on the next working day as follows.

CONFIDENTIAL

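### A treatment-related SAE suspends dosing only in its own cohort (Protocol 6.4.1), although all four cohorts receive the same VFI injection; a VFI-related SAE should pause every cohort until the safety review committee decides

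*Protocol*

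**What the plan says.** Protocol Section 6.4.1 opens with "Dosing in a cohort will be suspended if any of the following occur". The trigger at issue, one of three, is that "1 or more subjects in the dose cohort experience a treatment-related SAE". Both the count and the consequence are per cohort. The note under Table 6.1 gives the SRC further discretion over laboratory changes, again to suspend a cohort.

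Protocol Section 5.1.1 sets up the committee: "A safety review committee (SRC) will be convened at predetermined interval(s) to review safety data from this study". The intervals are not given. The SRC includes at least the investigator, the medical monitor and a medical representative of the sponsor. It is allowed to recommend measures up to "early termination of the study based on the discretion of the investigator or the criteria set forth in" Section 6.4. The closing sentence says that if there are no clinically significant AEs and "no evidence of signals upon review of the safety data, subsequent dosing of subjects and patients will be permitted".

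Protocol Section 9.4 covers any SAE: "site personnel will report it immediately by telephone to the medical monitor AND to the SAE hotline at ICON", and this is done "in accordance with procedures described in the study reference manual and/or SAE study-specific procedure". The section does not mention dosing, and the manual and procedure it names are not among the documents.

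Protocol Section 3.6.2 states a principle, "Subject safety will determine the progression or discontinuation of the study", and gives anaphylaxis as the reason for care over the order of dosing. SAP Section 10.1.13 plans no interim analysis and refers back to Protocol 5.1.1.

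**The concern.** A per-cohort rule is natural when cohorts differ in dose. Here they do not: Table 5.1 and Section 7.3 give every cohort the same VFI product at 47 mg per injection. The cohorts differ in renal function, in what accompanies VFI (albumin in Cohort 1, iohexol in Cohorts 2 to 4) and in the second dose given in Cohort 2.

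Sections 3.3 and 3.6.2 name acute anaphylaxis, with deaths reported for other dextran products, as the class risk. Neither section links it to renal function. If a subject had an anaphylactic SAE attributed to VFI, that information would concern the product, and so the next injection in any cohort.

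A hold in one cohort is right when the cause belongs to that cohort, such as the albumin infusion, the second dose, or slower FD001 elimination in Cohorts 3 and 4. Someone has to make that judgement before the next VFI dose elsewhere, and the protocol text does not require it. Two sites are involved (Synopsis: Cohorts 1 and 2 at one, Cohort 4 at the other, Cohort 3 at both), so the next dose could be given away from the site that saw the event.

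**Working it through.** **Texts side by side.** A cross-cohort hold would need one text with all three properties below.

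| Protocol text | Reaches other cohorts? | Triggered by an SAE? | Makes dosing wait? |
|---|---|---|---|
| 6.4.1 | No | Yes, if treatment-related | Yes, in the affected cohort |
| Note under Table 6.1 | No | No, laboratory changes | Only at SRC discretion |
| 5.1.1 | Yes | No, scheduled reviews, though an earlier meeting is not barred | No, the SRC may recommend; a clean review permits dosing |
| 9.4 | Yes, any SAE is reported | Yes | Not mentioned |
| 3.6.2 | Yes | No | Principle only |
| 7.3, spacing and sentinel pair | Spacing yes, sentinel pair Cohort 2 only | No | Sets the pace, not a stop |

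No row has all three.

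**Inputs for the counts.** Four cohorts of up to 8 (Section 10.1, Table 5.1); one VFI dose each, two in Cohort 2 (Table 5.1); at least 60 minutes between subjects, and in Cohort 2 a first pair whose second dose comes at least 24 h before the rest are dosed (Section 7.3); second dose at 24 h ± 1 h (Table 2.5, footnote c).

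**Planned size.** 4 × 8 = 32, which reproduces the stated figure. Planned VFI injections: 8 + 16 + 8 + 8 = 40.

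**Outside the mandatory suspension after an SAE in one cohort (maximum).**
- Subjects: 32 − 8 = 24.
- Injections: 40 − 8 = 32 if the SAE is in Cohort 1, 3 or 4; 40 − 16 = 24 if it is in Cohort 2.
- These maxima assume that no other cohort has yet dosed anyone. With a hold across all cohorts the number is 0 until the SRC decides.

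**Fastest dosing the spacing permits.**
- Single-dose cohort of 8: (8 − 1) × 60 min = 7 h from first to last subject.
- Cohort 2 at nominal times: the pair receive dose 1 at 0 and 1 h and dose 2 at 24 and 25 h; the other six start at 25 + 24 = 49 h and end at 54 h; their second doses run from 73 to 78 h.

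**Cohort 2 data at risk from a pause.**
- Most subjects between doses at once: 2 in the sentinel stage, 8 − 2 = 6 after it.
- Each subject's window closes 24 + 1 = 25 h after that subject's own first dose.
- If the six are dosed at the minimum spacing, the sixth first dose comes 5 × 60 min = 5 h after the first. If the SAE falls just then, 25 − 5 = 20 h remain before the first of the six leaves the window. A later SAE leaves less.

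**The case against.** The strongest reply is that study-level control already exists. The SRC reviews data from the whole study, a Section 6.4 trigger is a stated ground for recommending that the study end, and the dosing sentence in 5.1.1 uses both the protocol's usual word for Cohorts 1 and 2 and its usual word for Cohorts 3 and 4. A treatment-related SAE would fail the clean-review condition. The medical monitor sits on the SRC and is telephoned at once, and nothing bars an unscheduled meeting. All of this stands, and in practice someone would probably act. What it does not supply is an obligation: 5.1.1 is permissive and tied to scheduled reviews, and 9.4 is about reporting.

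A reader might infer that the 60-minute spacing is the only brake on dosing in other cohorts. The documents do not support that, because immediate reporting and the SRC's study-level authority are also brakes. Nor is the 7 h figure a forecast: it needs eight eligible subjects ready at once and no one acting on the telephone report.

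Prior experience is reassuring. The first-in-human study gave VFI to 6 × 4 = 24 subjects at up to 150 mg, and Phase 2a studied 33 patients; neither reported an SAE. This is a reason to rate the point low. It does not exclude a rare reaction: for 0 events in 24 + 33 = 57, assuming all 33 received VFI, the one-sided 95% upper bound is 1 − 0.05^(1/57) = 5.1%. Excluding subjects with dextran allergy or prior VFI exposure (6.2), the resuscitation team (3.3) and the crash cart (8.6.8) all lower risk, but they do not settle whether the next subject should be dosed.

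A reader might also infer that every treatment-related SAE should stop every cohort. That goes too far. Iohexol is given only in Cohorts 2 to 4 and albumin only in Cohort 1, so an iohexol reaction in Cohort 4 says nothing about Cohort 1. The trigger should be limited to VFI. Potential drug-induced liver injury is reported as an SAE under Section 9.6, so the rule must say where it falls.

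**Conclusion.** The point holds in a limited form. The protocol's only mandatory suspension after a treatment-related SAE is confined to the affected cohort, and no other text in the documents makes the remaining cohorts wait, although the product, the dose per injection and the named class risk are common to all four.

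Its size depends on timing. At most 24 of 32 subjects, and 24 to 32 of 40 planned injections, lie outside the mandatory suspension, and the real number depends on enrolment. If cohorts run one after another with an SRC review between them, the gap closes. If they overlap, it is open. The documents neither state nor exclude overlap. The study reference manual or SAE procedure may also contain a hold; if so, the protocol's stopping rule should match it.

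A reader might conclude that the protocol leaves the other cohorts without oversight after an SAE. It does not: the SRC and the medical monitor can act across the study. What is missing is the requirement that a decision be made and recorded before the next VFI dose. This is a cheap improvement.

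**What to change.** In Sections 6.4.1 and 5.1.1, state the following.

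- An SAE judged possibly or probably related to VFI (the Section 9.2.3 categories) in any cohort, including a potential drug-induced liver injury event so judged, pauses VFI dosing in all cohorts. This includes second doses in Cohort 2.
- The existing SRC is convened ad hoc and records a continue, hold or stop decision for each cohort before the next VFI dose.

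SAEs attributed only to iohexol or albumin stay under the per-cohort rule, as do the laboratory criteria and the moderate or severe AE rule. Because Section 9.2.3 rates relationship to study drug without naming the product, the investigator should rate it for VFI separately. Where VFI and iohexol cannot be told apart, the event counts as possibly VFI-related.

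The cost is about two sentences of protocol text, one unscheduled SRC call per VFI-related SAE, and a short pause in cohorts that may prove unaffected. The main loss is in Cohort 2: subjects between doses, at most six, could miss the 24 h ± 1 h window, which bears on the primary repeat-dose objective. That loss is new only when the SAE arises in another cohort, since 6.4.1 already suspends Cohort 2 for its own. A prompt SRC decision limits it; in the case worked above, a decision within 20 h keeps all six in window.

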##### **6.4.2 Individual Subject Stopping Criteria**

The individual subject stopping criteria are presented in [Table 6.1](#).

**Table 6.1 Individual Stopping Criteria**

Clinical Laboratory Parameter	Stopping Criteria
AST	$> 5 \times \text{ULN}$
ALT	$> 5 \times \text{ULN}$
Increase of $S_{cr}$	$> 1.5 \times \text{baseline}; > 1.5 \times \text{ULN}$

Subjects who have met one of the stopping criteria will continue with follow-up visits and PK/PD sampling unless the investigator or subject decides not to proceed.

Dosing of a cohort may be suspended on lesser changes in these parameters or change in other laboratory parameters at the discretion of the SRC.

CONFIDENTIAL

## 7 TREATMENT OF SUBJECTS

### 7.1 Identity of Investigational Product

The identity of the investigational product is presented in [Table 7.1](#).

**Table 7.1 Investigational Product**

Investigational Product	Dosage Form	Strength	Dose
Visible Fluorescent Injectate	Solution for injection	35mg FD001/12mg FD003	47 mg/3 mL

VFI will be sourced by FAST BioMedical. The VFI is packaged in a 10-mL, 20-mm clear glass vial with a 20-mm gray stopper and blue cap, and the product is a deeply colored lyophilized cake.

### 7.2 Identity of Comparator Products

The identity of the comparator products is presented in [Table 7.2](#).

**Table 7.2 Comparator Products**

Comparator Product	Dosage Form	Strength	Dose
Omnipaque 300 (Iohexol)	Solution for injection	647 mg of Iohexol equivalent to 300 mg of organic iodine per mL	5 mL

Comparator products will be sourced by the CRU.

Iohexol is packaged in a clear 10 mL bottle with a brown cap, and the product is a colorless to pale-yellow liquid. Each mL of Iohexol solution contains 1.21 mg tromethamine and 0.1 mg edetate calcium disodium.

### 7.3 Treatments Administered

Each subject will receive at least a single dose of the VFI, which will be administered IV through a bolus injection. Subjects in Cohort 1 will receive an infusion of 5% albumin (up to a maximum volume of 7 mL/kg over 30 minutes) 130 minutes after the dose of VFI in order to measure the increase in the subject's plasma volume using the FAST PV Technology.

An IV catheter will be inserted into the subject's arm. A single dose of VFI 47 mg/3 mL will be administered as a bolus injection through the catheter. A single dose of Iohexol 5 mL will be administered as a bolus injection through the same catheter 160 minutes after administration of VFI in Cohorts 2 through 4. Subjects in Cohort 2 will receive a second dose of VFI 47 mg/3 mL bolus injection 24 hours after the initial dose of VFI in order to assess the repeatability of the FAST mGFR Technology.

For safety reasons, the first 2 subjects in Cohort 2 will receive their second dose of VFI at least 24 hours before VFI dosing in the remaining subjects. Administration of VFI will be performed in a sequential manner with at least 60 minutes between each subject.

CONFIDENTIAL

A low-protein snack will be served prior to administration of the VFI (eg, toast, bagel or primarily carbohydrate based small portion). Water will be allowed as desired.

Standard meals will be served for Cohorts 1 and 2. Meals appropriate for the patient's medical condition will be served for Cohorts 3 and 4.

#### **7.4 Method of Assigning Subjects to Treatment Groups**

Eligible subjects/patients will be enrolled in a cohort based on renal function and will be assigned sequential subject numbers.

#### **7.5 Measurements of Treatment Compliance**

Investigational product will be administered by qualified healthcare professionals at the CRU as designated by the investigator. Details regarding dosing, including the dose administered and the date and time of dosing, will be recorded. The prepared syringes to be used for VFI and Iohexol injections will be weighed and documented before and after dosing in order to calculate the exact amount of product administered.

#### **7.6 Investigational Product Storage, Accountability, and Retention**

##### **7.6.1 Storage Conditions**

The VFI will be stored in a refrigerator at 2 to 8°C (36 to 46°F). Vials and glass or polymer bottles of Iohexol will be protected from strong daylight and direct exposure to sunlight and will be stored at controlled room temperature at 20 to 25°C (68 to 77°F); excursions are permitted to 15 to 30°C (59 to 86°F).

The VFI will be prepared within 60 minutes of dosing, and the prepared product will be stored at room temperature (25°C). The product will be protected from sunlight and ultraviolet light until dosing. The procedure for VFI preparation is located in [Appendix A](#).

Iohexol will be drawn into a syringe for administration and stored at room temperature (25°C).

The investigator will ensure that all the study drugs are stored and dispensed in accordance with Food and Drug Administration (FDA) regulations concerning the storage and administration of investigational drugs.

##### **7.6.2 Drug Preparation**

The procedure for reconstitution of the FAST VFI is located in [Appendix A](#).

#### **7.7 Packaging and Labeling**

##### **7.7.1 Study Drug**

The study drugs will be provided with appropriate labeling, including: sponsor name, address, and phone number, product name, active constituents, content by volume and number of units, batch number, expiry date, storage instructions, and the term "Caution: Investigational New Drug Limited by US Federal Law for Investigational Use Only."

CONFIDENTIAL

**7.7.2 Blinding of Treatment Assignment**

Not applicable. This is an open-label study.

**7.8 Concomitant Medications and Other Restrictions**

**7.8.1 Concomitant Medications**

For subjects in Cohorts 1 and 2, no concomitant medications (prescription, OTC, and herbal) may be administered, other than hormonal birth control, during the study unless they are prescribed by the investigator for treatment of specific clinical events (ie, AEs). However, for patients in Cohorts 3 and 4, maintenance medications as prescribed by their physicians are permitted. All medications (prescription and OTC), vitamin and mineral supplements, and herbs taken during the study will be documented on the concomitant medication electronic case report form (eCRF). Information recorded will include: start and stop dates and times, dose and route of administration, and indication. Medications taken for a procedure should also be included.

**7.8.2 Other Restrictions**

Subjects will be instructed to adhere to the following restrictions:

- Strenuous activity (as assessed by the investigator) is prohibited from 72 hours prior to admission until discharge from the CRU.
- Subjects are not permitted to consume alcohol from 24 hours prior to admission until discharge from the CRU.
- Subjects are not permitted to consume any food and drink from outside of the CRU while residing at the CRU.
- Subjects must comply with the CRU smoking policy, if applicable.
- Subjects are not permitted to participate in any other clinical trial or donate blood or plasma while participating in this clinical trial.

CONFIDENTIAL

## **8 STUDY ASSESSMENTS AND PROCEDURES**

Subjects will undergo study procedures and assessments at time points specified in the Schedules of Assessments and Procedures ([Table 2.1](#), [Table 2.2](#), and [Table 2.3](#)).

### **8.1 Medical and Surgical History**

The investigator or designee will collect a complete medical and surgical history at screening. Interim medical and surgical history will be collected at CRU admission to determine if any changes have occurred since screening. The medical history should include all active medical problems regardless of time of onset.

### **8.2 Demographic Characteristics**

Demographic characteristics including sex, age, race, and ethnicity will be recorded.

### **8.3 Physical Measurements**

Height (cm) and body weight (kg) without shoes will be recorded. Body mass index will be calculated using the height obtained at screening.

### **8.4 Pharmacokinetic Assessments**

#### **8.4.1 Drug Concentration Measurements**

Plasma PK samples will be collected at time points specified in the PK and PD Sampling Schedules ([Table 2.4](#), [Table 2.5](#), and [Table 2.6](#)). Blood sample collection, processing, and shipping details will be outlined in a separate study reference manual.

Plasma concentrations of FD001 and FD0003 will be determined using a validated fluorometric assay at MRIGlobal.

Urine concentrations of FD001 will be determined using a validated method and concentration of FD001 will be multiplied by urine volume to determine the amount of excreted FD001.

#### **8.4.2 Pharmacokinetic Parameters**

Pharmacokinetic parameters will be calculated from the plasma and urine concentration data using noncompartmental methods (Phoenix WinNonlin®, Version 6.3 or later, Pharsight Corporation, St. Louis, MO) and actual sampling times. The following PK parameters will be determined:

$C_{\max}$  Maximum observed plasma concentration

$t_{\max}$  The time that  $C_{\max}$  was observed

$AUC_{0-12}$  Area under the plasma concentration-time curve from time 0 to 12 hours; calculated using the linear/log trapezoidal rule (FD001 only)

CONFIDENTIAL

AUC last	Area under the plasma concentration-time curve from time 0 to the time of the last quantifiable concentration; calculated using the linear/log trapezoidal rule
AUC inf	Area under the plasma concentration-time curve from time 0 extrapolated to infinity; calculated as AUC last + C last /λ z , where C last is the last measurable concentration
AUC extrap	Area under the plasma concentration-time curve from the time of last observed concentration extrapolated to infinity expressed as a percent
t ½	Terminal elimination half-life; calculated as ln(2)/λ z
λ z	Terminal elimination rate constant
CL	Total body clearance; calculated as Dose/AUC inf
CL r0-2	Renal clearance from time 0 to 2 hours; calculated as Ae 0-2 /AUC 0-2 , where Ae 0-2 is the amount of FD001 excreted in the urine from time 0 to 2 hours (FD001 only)
CL r2-12	Renal clearance from time 2 to 12 hours; calculated as Ae 2-12 /AUC 2-12 , where Ae 2-12 is the amount of FD001 excreted in the urine from time 2 to 12 hours (FD001 only)
CL r0-12	Renal clearance from time 0 to 12 hours; calculated as Ae 0-12 /AUC 0-12 , where Ae 0-12 is the amount of FD001 excreted in the urine from time 0 to 12 hours (FD001 only)
V z	Volume of distribution during the terminal phase; calculated as CL/λ z
V ss	Volume of distribution at steady state; calculated as MRT inf × CL, where MRT inf is the mean residence time extrapolated to infinity
Ae 0-2	Amount of FD001 excreted unchanged in the urine from time 0 to 2 hours
Ae 2-12	Amount of FD001 excreted unchanged in the urine from time 2 to 12 hours
Ae 0-12	Amount of FD001 excreted unchanged in urine from time 0 to 12 hours

CONFIDENTIAL

Extrapolation methods will be used in Cohort 2, as needed, to correct concentration data after a second dose of FAST VFI in order to calculate PK parameters. Alternative methods (ie, compartmental modeling) may be used if extrapolation methods are inadequate. Computational details will be provided in a separate statistical analysis plan (SAP).

For the calculation of the FAST mGFR and PV in Cohort 2, residual levels of FD003 will be measured in the predose sample and those values subtracted from post-second-administration sample values to allow for a clean calculation of PV from dose 2. As these are healthy subjects we are not anticipating any level of residual FD001 that would affect the calculation of GFR.

